6.0 Analysis Plan

The variables to be considered in the protocol are described below.

Primary efficacy outcome variables:

- OSDI test score.

Secondary efficacy outcome variables:

- Changes in best corrected visual acuity (BCVA).
- Changes in corneal and conjunctival staining with lissamine green.
- Corneal and conjunctival staining changes with fluorescein.
- Changes in tear film break-up time (TRL) with fluorescein.

Security Variables

Primary Safety outcome variable:

- Incidence of unexpected adverse events (AEs) related to the drug.

Secondary safety outcome variable:

- Incidence of expected AEs.

Table 2. Operational Definition of the Variables

Variable	Definition Conceptual	Definition Operational	Scale of measurement	Category
Events adverse	Any event adverse adverse doctor that occurs in a patient or clinical research subject who was administered a collected through the pharmaceutical product and that, not necessarily has a relationship causal with this treatment.	The events adverse effects manifested during the conduct of the study will be electronic CRF.	• Nominal • Frequency: • Intensity: 0= Mild 1= Moderate 2= Severe • Causality: 0=Probably or possibly related. 1=Unlikely related.	Subjects presenting AE/Total number of exposed subjects.
Ocular Surface Disease Index Score (OSDI).	The OSDI is a questionnaire designed to establish a severity and classification of the dry eye according to its symptoms.	The evaluator will apply the questionnaire to the subject and allow him to do so answer in calm without any kind of pressure and/or coercion. See Annex 1. OSDI.	Continue	Score: $OSDI = \frac{(Suma\ del\ puntaje)25}{\# \ de \ respuestas \ contestadas}$
Changes in corrected visual acuity (BCVA).	Visual acuity corrected (BCVA) is a test of visual function. Spatial VA is the ability to distinguish separate elements of an object and identify them as a whole. It is	Booklet of Snellen	Quantitative discrete.	Fraction, normal value = 0.6 to 2.0

It quantifies the minimum angle of separation (located at the nodal point of the eye) between two objects that allows them to be perceived as separate objects.
				
Changes of corneal and conjunctival staining with green lissamine.	Detection of epithelial defects in the conjunctiva and cornea.	Observation direct with slit lamp, Oxford scale	Qualitative Ordinal	
Degrees:
 
The staining is presented in a series of panels (AE). The staining points range from 0-5 for each panel and from 0-15 for the total exposed area of conjunctiva and cornea.

		See Annex 2.		Oxford scale.
Corneal and conjunctival staining changes with fluorescein.	Detection of epithelial defects in the conjunctiva and cornea.	Direct observation with slit lamp and cobalt blue filter, Oxford scale	Qualitative Ordinal	
Degrees:
 
The staining is presented in a series of panels (AE). The staining points range from 0-5 for each panel and from 0-15 for the total exposed area of conjunctiva and cornea.

		See Annex 2.		Oxford scale.
Changes in tear film break-up time (TRPL) with fluorescein.	The stability of the Tear film is usually evaluated clinically by the TRL. This involves instilling fluorescein on the ocular surface to allow visualization of the tear film and measure the time it takes for the tear film to break up after the last blink.	It will be measured at end of a blink and you will be asked not to blink immediately until the tear film on the cornea breaks.	Quantitative continues.	Normal: > 10 seconds.

7.0 Methods of Analysis

Statistical analysis will be performed by staff of Laboratorios Sophia, SA de CV. The statistical program SPSS version 19.0 (IBM Corporation, Armonk, NY, USA) will be used.

The designated personnel will be blinded to the intervention groups. Coding will be performed using consecutive numbers for each intervention group.

The data will be collected and organized in an Excel spreadsheet (Microsoft® Office). The data will then be exported to the SPSS software platform. The variables will be categorized according to their nature (see Table 2).

Study participants will be identified by a number and their initials.

The initials of the subject of study will be obtained starting with the first letter of the name, followed by the first letter of the first surname and the first letter of the second surname, obtaining a maximum of three letters. In case the person has two names or a compound surname, the first letter will always be used.

Example:

to.	[name]	B. [name]
to.	Initials: AMC	b. Initials: JDO

Once the subject has been selected, they will be assigned a number that will identify them throughout the study. This code will consist of eight numbers in the following order from left to right:

- Three digits of the molecule under study according to the sponsor's designation.
- Two digits corresponding to the research center number.
- Three digits of the consecutive number assigned to its inclusion at the research center.

Subjects will be divided into two equal groups, which will be randomly and blindly assigned to one of the PI, PRO-176 or Systane® Balance (assignment 1:1). Which will be administered based on the dosage described in the protocol.

A preliminary safety analysis will be performed upon completion of follow-up of subject 12 in the Nanodrop® group (Phase I).

If fewer than 20% of unexpected drug-related AEs occur in the Nanodrop® group, enrollment for the efficacy analysis (Phase II) will be completed. Otherwise, the study will be terminated.

The results of the continuous quantitative variables will be presented in measures of central tendency: mean, standard deviation and ranges, see table 2.

The Kolmogorov-Smirnov and Shapiro Wilk test will be performed to determine whether the distribution is normal in the results obtained in each study group (Haffajee et al., 1983).

The statistical analysis of continuous **quantitative variables** to find significant differences (p) will be as follows:

- Intra-group analysis: will be determined using the Wilcoxon rank test, for quantitative variables (Woolson, 2008).
- Between-group analysis: differences between groups will be analyzed using the Student t-test or the Mann-Whitney U statistic if applicable (it will be used to test whether a group of data comes from the same population).

The level of difference to consider significance will be an alpha (α) of 0.05 or less. It will be considered a 95% CI for non-inferiority criteria (Schumi & Wittes, 2011; Easty et al., 2006).

The result of the nominal and ordinal qualitative variables will be presented in frequencies, proportions and percentages, see table 2.

Statistical analysis to identify significant differences in **qualitative variables** will be performed by creating 2x2 contingency tables and will be carried out as follows:

- Intra-group difference: McNemar's test (Klingenberg & Agresti, 2006). This test is applied to 2x2 contingency tables with a dichotomous trait, with matched subject pairs, to determine whether the marginal frequencies of the row and column are equal (marginal homogeneity).
- Difference between groups: Chi-square test (χ^2) Pearson's or Fisher's exact test in values expected under 5.

The level of difference to consider significance will be an alpha (α) of 0.05 or less.

For the reporting of adverse events, all eyes of participants who were randomized to an intervention group after the baseline visit will be considered.

The final results report will be displayed in tables or graphs, as appropriate.

Subjects who meet a minimum adherence of 70% will be included in the statistical analysis to meet the study objective, based on the weight of the PI. In cases where the container is not returned or has not been physically intact, adherence will be measured using the subject's diary.

The investigational drug will be considered safe and effective when there are no clinical and statistical differences in all primary outcome variables, with respect to its comparator.
(Systaine® Balance).

Table 3. Triangulation of concepts

Variable Type	Variable	A1	B1	B2	C1	C2	D1	E1	E2	E3
Background										
A1	Demographics						DT			
Basal										
B1	Medical record				DT					
B2	Comprehensive ophthalmological evaluation				DT		TB	TB		TB
Security										
C1	Unexpected/related AEs				TB		TB		TB	TB
C2	EAs				TB		TB		TB	TB
Effectiveness										
D1	OSDI				DB			DB		
Secondary outcome										
E1	MAVC				DB	TB	TB		DM	
E2	Ocular surface stains				DB	TB	TB		DM	
E3	Tear film time				DB	TB	TB			DM

D: Descriptive statistics; T: 2x2 contingency table; B: Bivariate analysis; M: Multivariate analysis.

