
 
- Nanodrop®. Propilenglicol 0.6%. Emulsión oftálmica.Laboratorios Sophia, S.A. de C.V.
 
- Posology:mínima a cumplir de 1 gota 4 veces al día, ambos ojos.
 
- Route of administration:Oftálmica.
 
	
Comparator product, dose and route of administration:	

 
- Systane® Balance. Propilenglicol 0.6%. Emulsión oftálmica.Alcon Laboratories, Inc.
 
- Posology:mínima a cumplir de 1 gota 4 veces al día, ambos ojos.
 
- Route of administration:Oftálmica.
 
	
Duration of treatment:	Approximate duration of the subject in the study:
28 días	35days
Evaluation criteria:	
Efficacy variables:	
Primary efficacy outcome variable:	

 
○ OSDI Test Score (Evaluation Time [ET]: day 29).
 
	
Secondary efficacy outcome variables:	

 
○ Changes in best corrected visual acuity (BCVA) (TE: day 8 and 29).
 
○ Changes in fluorescein tear film break-up time (TRPL) (TE: day 8 and 29)
 
○ Corneal fluorescein staining changes (TE: day 8 and 29).
 
○ Changes in conjunctival staining with lissamine green (TE: day 8 and 29).
 
	
Security variables:	
Primary safety outcome variable:	

 
○ Incidence of unexpected AEs related to the PI (TE: day 8 and 29).
 
	
Secondary safety outcome variable:	

 
○ Incidence of expected AEs (TE day 8 and 29)
 
	
Exploratory outcome variable:	

 
○ Average number of applications performed daily
 
	
Statistical methodology:	
Data will be expressed as measures of central tendency: mean, standard deviation, and ranges for quantitative variables. Qualitative variables will be presented as frequencies and percentages. Statistical analysis will be performed using the Student t test or the Mann-Whitney U test (if	

applicable) for quantitative variables to determine the difference between groups. Differences between qualitative variables will be analyzed using the  $X^2$  (Chi-square) test or Fisher's exact test. A 95% CI will be considered for non-inferiority criteria based on the study objectives, with an  $\alpha < 0.05$  considered significant.

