#### 3.1.2 Primary efficacy objective

To demonstrate the non-inferiority of Nanodrop® compared to Systane® Balance in the treatment efficacy of patients with dry eye, using the OSDI (Ocular Surface Disease Index) test score.

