### 3.4.2 Efficacy hypothesis

$H_0$  = Nanodrop® is inferior to Systane® Balance by more than 5 points on the OSDI test score

$$H_0: \mu_A - \mu_B > \delta$$

$H_1$  = Nanodrop® is inferior to Systane® Balance by 5 points or less on the OSDI test score

$$H_1: \mu_A - \mu_B \leq \delta$$

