### 10.1.2 Data interpretation

The Kolmogorov-Smirnov and Shapiro-Wilk tests will be performed, as applicable, to determine whether the distribution is normal in the results obtained in each study group.

The results of continuous quantitative variables will be presented in measures of central tendency: mean, standard deviation and ranges.

The statistical analysis of continuous quantitative variables to find significant differences (  $p<0.05$  ) will be as follows:

- Intra-group analysis: will be determined using the Wilcoxon rank test for quantitative variables.
- Between-group analysis: Differences between groups will be analyzed using the Student t-test or the Mann-Whitney U statistic if applicable ( it will be used to test whether a group of data comes from the same population).

The level of difference considered significant will be an alpha ( $\alpha$ ) of 0.05 or less. A 95% CI will be considered for noninferiority criteria.

The results of the nominal and ordinal qualitative variables will be presented in frequencies, proportions and percentages.

Statistical analysis to identify significant differences in qualitative variables will be performed by creating 2x2 contingency tables and will be carried out as follows:

- Intra-group difference: McNemar's test. This test is applied to 2x2 contingency tables with a dichotomous trait, with matched pairs of subjects, to determine whether the marginal frequencies of the row and column are equal (marginal homogeneity).

- Difference between groups: Pearson's Chi-square test (  $X^2$  ) or Fisher's exact test for expected values less than 5.

The level of difference to consider significance will be an alpha ( $\alpha$ ) of 0.05 or less.

For adverse event reporting, all eyes of participants randomized to an intervention group after the baseline visit will be considered. Results will be expressed as the number of subjects.

The final results report will be displayed in tables or graphs, as appropriate.

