5.0 Sample Size Calculation

For the sample size calculation, changes in the OSDI (*Ocular Surface Dehydration Index*) questionnaire score were considered, in studies with ocular lubricants in patients with dry eye disease (DED), as the primary efficacy variable.

PRO-176 (Nanodrop®; Laboratorios Sophia, SA de CV) is expected to be non-inferior to its comparator (Systane® Balance; Alcon Research Ltd, Fort Worth, TX, USA), according to the following working hypotheses:

$$H_0: \varepsilon \leq \delta$$

$$H_1: \varepsilon > \delta$$

Where $\mu_A - \mu_B = \varepsilon$, is the true difference in means between the test treatment (PRO-176) and the active control (Systane® Balance). Where δ is the non-inferiority margin, and the ratio of the sample sizes between the two groups is given by:

$$k = \frac{n_A}{n_B}$$

Calculations were performed using the non-inferiority equation for two means and for statistical power (Chow et al., 2008).

$$n_A = kn_B \text{ y } n_B = \left(1 + \frac{1}{k}\right) \left(\sigma \frac{z_{1-\alpha} + z_{1-\beta}}{\mu_A - \mu_B - \delta} \right)^2$$

$$1 - \beta = \theta(z - z_{1-\alpha}) + \theta(-z - z_{1-\alpha}) , \quad z = \frac{\pi_A - \pi_B - \delta}{\sigma \sqrt{\frac{1}{n_A} + \frac{1}{n_B}}}$$

Where σ is the standard deviation, $k=nA/nB$ is the agreement ratio, θ is the standard Normal distribution function, α is the type I error (confidence interval), β is the type II error (meaning that $1-\beta$ corresponds to the power) and δ is the test margin.

With a power of 80% ($\beta=0.20$), a significance level of 0.05 (α) and a non-inferiority margin (δ) of -5 points on the OSDI score (Grubbs et al., 2014; Labetoulle et al., 2017; Pérez-Balbuena et al, 2016).

The calculation was based on the study by Benitez-Del-Castillo et al., 2016. Phase I and II clinical study. A total of 156 healthy subjects and patients with DED were enrolled. The Phase I study included 30 healthy volunteers; it was a single-center, parallel-group, open-label study. Phase II was a multicenter, double-blind study. In Phase I, SYL1001 was administered at 1.125% and 2.25% doses, and in Phase II, at 0.375% and 0.75%. After 10 days of treatment, the primary efficacy variable was the effect on the OSDI score. OSDI scores were significantly reduced compared to baseline ($p<0.01$) for all treatments in both Phase I and Phase II. No statistical differences were observed between treatments.

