The sample size calculation was performed considering a reduction in the OSDI score of 17.6 points for the placebo group at their final visit versus a reduction of 16.5 points for the treated group. Considering a δ of 17.1, a similar reduction in the OSDI score is expected for both treatments, with no statistically significant differences at their final visit.

The calculation was performed using the online tool: <http://powerandsamplesize.com>.

The estimated sample size was 101 subjects (51 subjects per arm), which was increased by 25% to account for potential losses (25 subjects). The estimated number of subjects (both eyes) was 126.

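### SAP 7.0 declares efficacy when no difference is found, which contradicts the non-inferiority objective and would often pass a product at or beyond the 5-point margin

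*SAP*

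**What the plan says.** The primary efficacy objective (Protocol 3.1.2; SAP 2.0 agrees) is "To demonstrate the non-inferiority of Nanodrop® compared to Systane® Balance in the treatment efficacy of patients with dry eye", measured by OSDI. Protocol 3.4.2 sets the null hypothesis as "Nanodrop® is inferior to Systane® Balance by more than 5 points on the OSDI test score". SAP 5.0 sizes the trial with "a significance level of 0.05 (α) and a non-inferiority margin (δ) of -5 points on the OSDI score".

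The decision criterion is stated in two incompatible ways:

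- **Confidence interval.** SAP 7.0: "It will be considered a 95% CI for non-inferiority criteria". Protocol 10.1.2: "A 95% CI will be considered for noninferiority criteria". The Synopsis (statistical methodology) says the same. None of these says which limit is compared with which value, or whether the interval is one- or two-sided.
- **No difference.** Near the end of SAP 7.0: "The investigational drug will be considered safe and effective when there are no clinical and statistical differences in all primary outcome variables", relative to the comparator.

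The second is the only explicit success statement in either document, and the protocol has no counterpart. The tests named for OSDI (Student t or Mann-Whitney U in SAP 7.0, Mann-Whitney U in Protocol Table 2) are tests for a difference.

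**The concern.** A non-significant test does not show that a deficit is smaller than 5 points. It may only show that the trial was too small or too variable to detect one. Under a no-difference rule, smaller arms and noisier data make success easier, which is the reverse of what non-inferiority requires.

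Nothing says which criterion governs, and they can give opposite answers on the same data. An analyst who follows the explicit sentence could declare the product effective when the confidence interval extends well past the margin. The rule also errs in the other direction, because a significantly better product fails a requirement of no statistical difference.

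**Working it through.** **Inputs.** SD 17.1 (Protocol 10.2.2, as σ; SAP 5.0 prints the same value under δ). It is tied to OSDI reductions and is assumed here to hold for day-29 scores. Margin 5 points (Protocol 3.4.2). Alpha 0.05, taken as two-sided for the difference test. Evaluable subjects per arm: 51 (Protocol 10.1.4) or 63 (Synopsis). Assumed reductions: 17.6 in the comparison group "versus a reduction of 16.5 points for the treated group", a deficit of 1.1.

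**The plan's own sample size.** The formula in both documents is n per arm = 2 × (σ(z₁₋α + z₁₋β)/distance to margin)². With one-sided alpha 0.05 and 80% power, 17.1 × (1.645 + 0.842) = 42.5.

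- Distance 5 − 1.1 = 3.9: 238 per arm.
- Distance 5.0: 145 per arm.
- Distance 6.0: 101 per arm. Distance 6.1: 98 per arm.

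The SAP's total of 101 (51 per arm) is not reproduced. The formula gives 101 only as a per-arm figure at distance 6.0, and 51 per arm appears there only if the factor (1 + 1/k) is dropped. This is a separate matter, but it explains why power is low under a CI rule.

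**Precision.** SE = 17.1 × √(2/n) = 3.386 (n = 51) or 3.047 (n = 63). The two-sided 95% half-width is 6.72 or 6.03; the one-sided 95% half-width is 5.62 or 5.05. All exceed the margin. At this SD even an observed tie fails either CI rule, yet it satisfies the no-difference rule.

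**One data set, two verdicts.** With 63 per arm and Nanodrop observed 4 points worse, the two-sided 95% CI is 4 ± 6.03, or −2.0 to +10.0. The one-sided upper bound is 4 + 5.05 = 9.05. The difference is non-significant and below 5 points, so SAP 7.0 passes it. Both CI rules fail it.

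**Pass probabilities.** Let D be the observed difference, D ~ N(d, SE²), analysed with a pooled-variance t-test on 2n − 2 degrees of freedom. At d = 5 the noncentrality is 5/3.386 = 1.48 or 5/3.047 = 1.64. Each cell gives n = 51 / n = 63.

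| True deficit | Non-significant | Non-significant and \|D\| < 5 | Upper limit < 5, two-sided 95% CI | Upper limit < 5, one-sided 95% bound |
|---|---|---|---|---|
| 5 | 69% / 63% | 50% / 50% | 2.5% / 2.5% | 5% / 5% |
| 7.5 | 41% / 31% | 23% / 21% | under 0.5% | under 1% |
| 1.1 | 94% / 94% | 84% / 88% | 21% / 25% | 31% / 36% |

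Mann-Whitney, by simulation at d = 5, gives about 70% and 64% non-significant.

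At the 1.1-point deficit, the share of trials in which SAP 7.0 passes the product and the CI rule does not is 74% / 70% (two-sided) or 64% / 59% (one-sided). With |D| < 5 also required it is 67% / 66% or 57% / 55%.

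**Joint verdict.** The sentence also covers unexpected related adverse events. If true rates are equal and between 0 and 20%, that comparison is significant in 0–5% of trials. At d = 5 the joint pass rate on non-significance is therefore about 60% (0.63 × 0.95) to 69%.

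**Better product.** If Nanodrop is truly 5 points better, the difference is significant, so the rule fails it, in 1 − 0.69 = 31% or 1 − 0.63 = 37% of trials.

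**The case against.** The strongest defence is that the sentence requires no clinical difference as well as no statistical one, and that it closes the section that sets the CI criterion. The only OSDI difference threshold stated for comparing the arms is the 5-point margin. The clinical part could therefore mean that the confidence limit clears the margin. SAP 7.0 would then only add a condition to the CI rule, and a product 5 points worse would pass in 2.5–5% of trials. Everything else in the documents also points to non-inferiority, and the analysts are blinded.

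Some of this stands. The term is undefined, so the pass rate at a 5-point deficit runs from 2.5% to 69% depending on the reading. The 50% follows from our assumed point-estimate cut-off and would be near one half at almost any sample size. At a true 1.1-point deficit the product is within the margin, so CI-rule failures there reflect low power and not a false SAP verdict. The 1.1 also depends on reading the treated group as Nanodrop. With 1.1 points in Nanodrop's favour, CI-rule power would be 43–51% two-sided or 56–64% one-sided.

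The defence does not rescue the sentence. It supplies a rule the text does not contain, and that rule does not fit the adverse-event outcome governed by the same words. Even so read, the no-statistical-difference condition would still fail a better product. Blinding limits selective choice between criteria; it does not correct a wrong rule followed faithfully.

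**Conclusion.** The concern holds, and the sentence must be corrected. As written, the only explicit efficacy criterion is one of no difference, in conflict with the objective, the hypotheses and the CI criterion. For a product exactly at the margin it gives a pass in 63–69% of trials on non-significance alone, or about 50% with a 5-point cut-off on the observed difference, against 2.5–5% for a margin-based CI rule. At 7.5 points worse it still passes 31–41% (21–23% with the cut-off).

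These figures rest on SD 17.1 applying to day-29 scores, 51–63 evaluable subjects per arm, normal data and a two-sided 0.05 test. They cover OSDI only, so they are upper bounds for the joint safety and efficacy verdict. The 2.5–5% range reflects the unstated sidedness of the interval: the sample-size formula uses z₁₋α at alpha 0.05, a one-sided 5% test, which a two-sided 95% CI does not match.

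**What to change.** Remove the sentence as it applies to efficacy and state one governing rule. For example: non-inferiority is concluded only if the upper limit of the two-sided 95% CI for Nanodrop minus Systane Balance in mean day-29 OSDI (higher is worse) is below +5 points, and a p-value for difference plays no part.

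With it:

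- State the sidedness of the CI and use the matching alpha in the sample size.
- State whether ε is a difference in scores (Protocol 3.4.2) or in reductions (SAP 5.0, where ε > −5 is coherent). Correct Protocol 10.2.2, which labels both hypotheses H₀ and pairs ε ≤ δ with a margin of −5.
- Align the OSDI test in Protocol Table 2 with the CI rule.
- Reconcile the safety half of the sentence with Protocol 3.4.1, which sets a 20% threshold within the Nanodrop group, not a comparison between arms.

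The cost is wording in SAP 5.0 and 7.0 and Protocol 3.4.2, 7.4.4 and 10.2.2. The rule needs no new data, visits or software. The real consequence is power. Under this rule at a 1.1-point deficit it is 21–25% (31–36% with a one-sided bound), so the stated 80% must be restated or the sample size revisited. By the documents' formula, 80% power needs about 238 per arm (one-sided 5%) or 302 (two-sided 95% CI) at a 1.1-point deficit, and 145 or 184 at zero difference, against 63 planned.
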